10.3.1 Definition and recording of safety-relevant events

An adverse event (ADVERSE EVENT) AE) is any unfortunate medical occurrence in a study subject who is exposed to a simulated or terrestrial altitude (as listed in Chapter 8.1.1) that is not necessarily causally related to the study process. An AE can therefore be any adverse and unintentional sign or symptom that can be related to the intervention product (according to Chapter 8.1.1).

According to swissethics.ch, a serious adverse event (SAE) is classified as any unfortunate medical occurrence that results in death, is life-threatening, requires or prolongs hospitalization of the subject, results in a persistent or significant disability/inability, or is a congenital anomaly/birth defect. In our

SUPSI

study, an SAE is not to be expected due to the amount that is being investigated.

The equipment used in this study is used in accordance with the operating manual.

If the examination leads to a reaction described above, this is classified as a safety-relevant event by the study leader. For the affected study participant, the study is completed at this time, and the data already collected will be processed as described in chapters 7.4 and 9.1.6.

The subject-specific demographic data collection sheet (page 4) records:

- Date and time of the incident
- Course of the incident
- Persons involved & witnesses
- Study ID (specified by the CEC)
- Personal data of the person concerned (if not previously recorded)

10.3.2 Reporting of Safety related events

Pursuant to Art. 37, 43 paras, 1&2 and Art. 63 Clin V.

10.3.3 Notification of a security-relevant event

A safety-related event is logged and immediately reported to the sponsor investigator (head of the research laboratory), study management and supervisor of the study.

The CEC will be informed as soon as possible and appropriate changes will be made to the protocol of the study. Further explanations can be found in chapter 2.10. Safety and protective measures must be reported to the responsible CEC within two days.

The report continues to the business liability insurance (Basler Versicherung) of Thim van der Laan AG in Landquart.

SUPSI

11 STATISTICAL METHODS

11.1 Hypotheses & Factors

Psychophysiological changes under simulated and terrestrial altitude.

Perfusion of skin microcirculation

- H0 The perfusion of the skin microcirculation does not change significantly at the simulated altitude compared to the terrestrial altitude.
- H1 The perfusion of the skin microcirculation changes significantly in the simulated altitude compared to the terrestrial altitude.

Oxygen saturation of the muscles and brain

- H0 The oxygen saturation of the muscles and the brain does not change significantly at the simulated altitude compared to the terrestrial altitude.
- H1 The oxygen saturation of the muscles and the brain changes significantly in the simulated altitude compared to the terrestrial altitude.

Oxygen saturation of the blood

- H0 The oxygen saturation of the blood does not change significantly in the simulated altitude compared to the terrestrial altitude.
- H1 The oxygen saturation of the blood changes significantly in the simulated altitude compared to the terrestrial altitude.

Blood pressure and heart rate

- H0 Blood pressure and heart rate do not change significantly at the simulated altitude compared to the terrestrial altitude.
- H1 Blood pressure and heart rate change significantly at the simulated altitude compared to the terrestrial altitude.

Skin temperature

- H0 The skin temperature does not change significantly at the simulated altitude compared to the terrestrial altitude.
- H1 The skin temperature changes significantly at the simulated altitude compared to the terrestrial altitude.

Lactate and creatine kinase

- H0 Lactate and creatine kinase do not change significantly at the simulated altitude compared to the terrestrial altitude.
- H1 Lactate and creatine kinase change significantly in the simulated altitude compared to the terrestrial altitude.

Equilibrium

- H0 The equilibrium does not change significantly at the simulated altitude compared to the

SUPSI

terrestrial altitude.

- H1 The equilibrium changes significantly in the simulated altitude compared to the terrestrial altitude.

Pain sensation

- H0 The sensation of pain does not change significantly in the simulated altitude compared to the terrestrial altitude.

- H1 The sensation of pain changes significantly in the simulated altitude compared to the terrestrial altitude.

Sleep disorder

- H0 The quality of sleep does not change significantly at the simulated altitude compared to the terrestrial altitude.

- H1 The quality of sleep changes significantly in the simulated altitude compared to the terrestrial altitude.

Symptoms of altitude sickness

- H0 The simulated altitude does not lead to any symptoms of altitude sickness compared to the terrestrial altitude.

- H1 The simulated altitude leads to symptoms of altitude sickness compared to the terrestrial altitude.

Dyspnea

- H0 The simulated altitude does not lead to dyspnea symptoms compared to the terrestrial altitude.

- H1 The simulated altitude leads to dyspnea symptoms compared to the terrestrial altitude.

State of mind

- H0 The simulated altitude does not lead to any changes in mood compared to the terrestrial altitude.

- H1 The simulated altitude leads to changes in state of mind compared to the terrestrial altitude.

Sleepiness

- H0 The simulated altitude does not lead to any drowsiness symptoms compared to the terrestrial altitude.

- H1 The simulated altitude leads to drowsiness symptoms compared to the terrestrial altitude.

Cognition

- H0 The simulated altitude does not lead to any cognitive changes compared to the terrestrial altitude.

SUPSI

- H1 The simulated altitude leads to cognitive changes compared to the terrestrial altitude.

Thermal comfort and temperature perception

- H0 The thermal comfort and the temperature perception do not change significantly in the simulated altitude compared to the terrestrial altitude.
- H1 Thermal comfort and temperature perception change significantly in the simulated altitude compared to the terrestrial altitude.

A 2-factor analysis is carried out.

Factor 1: Situation (simulated altitude vs. terrestrial altitude)

Factor 2: Time (baseline, after step-up task, 0, 5, 10, 15, 20, 25, 30 min post-cold water immersion of the hand) or

Time (baseline, post-cold water immersion of the hand)

Explanations for the hypotheses:

It has already been established that hypobaric hypoxia can have a negative impact on postural stability in the antero-posterior plane, compared to normobaric hypoxia. This indicates that the change in pressure per se can play a more important role compared to hypoxia (Degache et al. 2012). However, it must also be mentioned that visual acuity (the view) can also influence postural stability. Movements that occur and are processed unconsciously can activate muscles that play a role in postural control (Brandt et al. 1986). This factor is kept as low as possible during the measurement during the stay in the SAC hut by the test subject looking at the wall (as in the laboratory) and not into the distance (through a window, for example).

Regarding oxygen saturation, measured with a pulse oximeter as in our study, the study by Savourey et al. 2003 and Self et al. 2011 showed that these values were lower in the hypobaric hypoxia situation compared to the simulated altitude. These differences were already evident after short-term exposure and comparable (simulated) altitude exposures to our study. For the cardiovascular differences, Faiss et al. 2013, Miyagawa et al. 2011 and Self et al. 2011 showed that heart rate and blood pressure increased after short-term exposure at terrestrial altitude, compared to the simulated altitude.

Based on these results for oxygen saturation, heart rate and blood pressure, it stands to reason that the inflammation and lactate levels in the terrestrial study group are higher after submaximal exercise compared to the values in the simulated altitude group. However, we would like to investigate this hypothesis in our experiment.

Altitude sickness symptoms, which are very often studied in this field of research, showed the following differences: The risk or development of altitude sickness seems to be greater at terrestrial altitude compared to simulated altitude (Loeppky et al. 2005, Miyagawa et al. 2011). The difference between terrestrial altitude and simulated altitude on sleep quality was also investigated. In both initial positions, oxygen transport is significantly suppressed during the sleep phase. However, the simulated height in this case is a continuous (during the sleep phase) situation (Berssenbrugge et al. 1983). Millet et al. (2012), on the other hand, described that the ventilation of the lungs, and consequently the CO₂ content in the blood, are lower at the terrestrial altitude, compared to the simulated altitude. Poor sleep at terrestrial altitude could also have a negative effect on the daily state of mind as well as on drowsiness. Furthermore, the reduced oxygen saturation or the increased CO₂ content in the arterial blood could

SUPSI

lead to a reduction in oxygen saturation in the muscles and brain (and reduced cognitive performance) in the terrestrial situation. However, it must be explicitly mentioned that a direct comparison can only be made here if the simulated and also the terrestrial altitude are carried out in the same amount of time.

Thermal comfort and temperature perception are largely dependent on the outside temperature. The room temperature in the SAC hut is therefore adapted as much as possible to the conditions of the laboratory in order to keep this disturbing factor as low as possible. However, the different temperature in the 2 scenarios could also have an impact on the perfusion of the skin's microcirculation. Furthermore, it was described that sympathetic tone is increased at terrestrial altitude compared to simulated altitude. Catecholamines, such as norepinephrine, also seem to be released more frequently at terrestrial altitudes (Mazzeo et al. 1994).

The result of Noel-Jorand et al. 1996 is interesting. These authors described that the sensation of pain is largely dependent on the hypoxia itself and not only on the difference in air pressure. The pain threshold has decreased in this study and sensory discrimination has increased below terrestrial altitude. Hypoxia and the resulting adaptation to the lack of oxygen itself seem to be the main reason for this (Noel-Jorand et al. 1996).

There are several mechanisms that could explain the different reactions of terrestrial and simulated altitude. It is obvious that the difference in air pressure and the duration of the hypoxic situation are the primary factors, which are different in these 2 scenarios. However, these different factors themselves provide information about psychophysiological effects and therefore provide the impetus for further discussions in this field of research. The different room temperatures could also have an influence on the reactions of the test subjects. In this point, we will try to keep the ambient temperature as similar as possible. We are aware that other factors such as contact with other people in the SAC hut, the view, etc. can influence the results. We will control these disruptive factors as best we can. However, it is also important to record these factors and bring them forward as discussion points in the study.

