Skin temperature is measured via the iButton system (www.ibuttonlink.com). The self-adhesive sensors transmit the information about the skin temperature wirelessly to a computer. Furthermore, the skin temperature is recorded by means of a thermal imaging camera (FLIR). This measurement is measured during the baseline measurements, after the step-up task and up to 30 min after the cold water bath of the hand (5 min interval).

Lactate and creatine kinase

The lactate and creatine kinase measurement are carried out by capillary blood measurement (Accutrend, Roche Diagnostic, Rotkreuz, Switzerland & Reflotron, Roche Diagnostic, Rotkreuz, Switzerland). The affected area is disinfected and a superficial wound is pierced to take capillary blood. This measurement is measured during the baseline measurements, after the step-up task and up to 30 min after the cold water bath of the hand (5 min interval).

Balance measurement

The fluctuations of the hull are recorded and evaluated with the Sway Star™ System (www.b2i.info). The Sway Star™ is a measuring instrument that contains gyroscopes. It is attached to a belt that is placed around the patient's waist. The data is evaluated with the associated Sway Star™ software and transferred to the data sheet. This measurement is carried out after the baseline measurement and after the cold water bath immersion of the hand.

SUPSI

Figure: Measuring balance with the Sway Star™

Pain sensation

The pain threshold is measured using a pain pressure algometer (NOD, www.to-nod.com). As soon as the patient reports pain, this measurement is stopped. This measurement is carried out after the baseline measurement and after the cold water bath immersion of the hand.

Psychological measurements

The psychological measurements (sleep disorder, altitude sickness, dyspnea, state of mind, drowsiness) are evaluated on the basis of written questionnaires.

The cognitive test battery consists of 8 tasks (ANAM, US Department of Defence, Vista Life Sciences, USA), which are carried out on a laptop computer.

These measurements are carried out after the baseline measurement and after the cold water bath immersion of the hand.

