8.2.1 Experimental intervention

Simulated height: The test subjects are in the laboratory of our institution and are connected to Cloud 9 by means of a mask. The subjects are exposed to a simulated altitude of 3530 m above sea level under normobaric conditions. This intervention is used to determine the psychophysiological effect under normobaric and hypoxic conditions.

Terrestrial altitude: The subjects are at an SAC hut (Bergrestaurant Hohsaas: <https://www.hohsaas-bergrestaurant.ch>) in the canton of Valais at an altitude of 3200 m above sea level. By means of this

SUPSI

exposure, the psychophysiological effect under hypobaric and hypoxic conditions is determined. The test subjects spend a single night in this SAC hut and the measurements are repeated the next day.

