
Blood Pressure & Heart Rate Skin temperature Lactate & Creatine Kinase
 
10 min
 
3.) Cold water immersion of the hand
 
5 min
 
4.) Follow-up Perfusion Microcirculation Oxygen Saturation Muscle & Brain Oxygen saturation of blood Blood Pressure & Heart Rate Skin temperature Lactate & Creatine Kinase Balance measurement Pain sensation Psychological measurements Thermal comfort & temperature perception
 
40 min
	
Skin temperature Lactate & Creatine Kinase
 
10 min
 
3.) Cold water immersion of the hand
 
5 min
 
4.) Follow-up Perfusion Microcirculation Oxygen Saturation Muscle & Brain Oxygen saturation of blood Blood Pressure & Heart Rate Skin temperature Lactate & Creatine Kinase Balance measurement Pain sensation Psychological measurements Thermal comfort & temperature perception
 
40 min
	
Skin temperature Lactate & Creatine Kinase
 
10 min
 
3.) Cold water immersion of the hand
 
5 min
 
4.) Follow-up Perfusion Microcirculation Oxygen Saturation Muscle & Brain Oxygen saturation of blood Blood Pressure & Heart Rate Skin temperature Lactate & Creatine Kinase Balance measurement Pain sensation Psychological measurements Thermal comfort & temperature perception
 
40 min

---	---	---

Test log	Time exposure	Visits
Declaration of Consent	30 min	Unique
Simulated Height	20 + 90 min = 110 min	Unique
Terrestrial Altitude	20 + 90 min = 110 min	Twice (incl. 1x overnight stay)
Control intervention	20 + 90 min = 110 min	Unique
TOTAL TIME COMMITMENT	470 min + 1 night	

Each test subject can expect a total time expenditure of 470 minutes excluding the journey to and from Valais and the overnight stay at the SAC mountain hut.

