2.2 Intervention

The subject is then exposed to either the simulated altitude or the normobaric & normoxic situation. Afterwards, a step-up task of 5 minutes and a cold water bath immersion of the hand for 5 minutes is performed. In the terrestrial situation, the subject is measured at the time of arrival at the SAC Hut, as well as the following day after an overnight stay at the SAC Hut. The experimental procedure is therefore illustrated:

[figure not shown]

Illustration of the experimental process

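### The sleep hypothesis for simulated versus terrestrial altitude cannot be tested, and the plan does not say which of the two hut visits counts as terrestrial

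*Combined protocol and SAP*

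**What the plan says.** Section 4.2 lists the sleep disorder questionnaire among the primary parameters, and section 11.1 gives it its own pair of hypotheses: "H1 The quality of sleep changes significantly in the simulated altitude compared to the terrestrial altitude".

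The visit table in section 9.1 gives simulated altitude a single session of "20 + 90 min = 110 min" and lists the hut as "Twice (incl. 1x overnight stay)". Section 8.2.1 says of the hut: "The test subjects spend a single night in this SAC hut and the measurements are repeated the next day". Section 9.2.2 (item 2.2, Intervention) gives the timing: "the subject is measured at the time of arrival at the SAC Hut, as well as the following day after an overnight stay". The visit table shows no other overnight stay.

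On the psychological questionnaires, section 5.1 says: "These measurements are carried out after the baseline measurement and after the cold water bath immersion of the hand". Sections 11.1 and 11.4.2 analyse them with two factors: Situation (simulated, terrestrial) and Time (baseline, post-immersion). There is no term for hut day.

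The explanatory text in section 11.1 cautions that "a direct comparison can only be made here if the simulated and also the terrestrial altitude are carried out" for an equal length of time. A later paragraph concedes that the duration of hypoxia differs between the two scenarios.

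**The concern.** There are two linked problems.

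First, a sleep score taken in the simulated session can only describe a night spent somewhere else. The same is true of a score taken on arrival at the hut. A difference between simulated and terrestrial values can be computed, but it is not a difference in sleep quality between two kinds of altitude. The Time factor adds nothing, because nobody sleeps between its two readings.

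Second, three altitude sessions (one simulated, two at the hut) have to fit into a factor with two levels. If the next-day visit fills the terrestrial level, alone or averaged with arrival, the contrast carries the night, the longer hypoxia and the repeat testing as well as the type of altitude. Section 11.1 itself suggests that poor sleep at the hut may affect mood and drowsiness, so the problem reaches beyond the sleep outcome. An unspecified comparator also leaves the visit open to choice once results are known.

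**Working it through.** **Sessions and nights.** Inputs are from the section 9.1 table: consent 30 min, simulated 1 × 110, hut 2 × 110, control 1 × 110.

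- Total: 30 + 110 + 220 + 110 = 470 min. This reproduces the plan's figure: "Each test subject can expect a total time expenditure of 470 minutes".
- Nights: 0 under simulated altitude, 1 at the hut. Of the 4 measured sessions, only the second hut session follows sleep at altitude.

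**Length of simulated hypoxia.** The listed steps sum to 20 + 5 + 10 + 5 + 40 = 80 min, within the stated maximum of 90.

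- Synopsis: the mask goes on after the 20-minute acclimatization and before baseline, giving 80 to 90 min.
- Section 9.2.2: exposure is described after the baseline measurement, giving 80 − 20 = 60 to 90 − 20 = 70 min.

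The two descriptions should be reconciled. On either, hypoxia lasts under two hours and includes no sleep.

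**Share of outcomes.** Section 4.2 lists 10 objective parameters, pain sensation and 6 psychological measures: 10 + 1 + 6 = 17. Sleep, the one outcome that is strictly untestable, is 1 of 17. The unspecified hut visit affects every simulated-versus-terrestrial test.

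**Choosing the hut visit after seeing the data.** Let H1 and H2 be the hut visits and S the simulated session, with equal variances. Let the hut visits correlate at a with each other and at b with S. Then

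corr(H1 − S, H2 − S) = (1 + a − 2b) / (2(1 − b)).

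If a = b this is 0.5; if a > b it is higher. For example, a = 0.8 and b = 0.5 give 0.8. The chance that at least one of two two-sided 5% tests rejects under the null (bivariate normal) is:

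| Correlation of contrasts | Type I error |
|---|---|
| 0 (independence bound, 1 − 0.95²) | 9.75% |
| 0.5 | 9.1% |
| 0.8 | 7.8% |

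**If the next-day visit is used (illustration).** Assume no true difference between altitude types, n = 24, and a two-sided 5% paired t-test. Let the night or longer stay shift the result by d standard deviations of the paired difference. The noncentrality is d√24 on 23 degrees of freedom. Averaging both hut visits halves the shift; the same standard deviation is assumed.

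| d | Next day vs simulated: rejects | Both hut visits averaged: rejects |
|---|---|---|
| 0.2 | 16% | 8% |
| 0.3 | 29% | 11% |
| 0.5 | 65% | 22% |
| 0.8 | 96% | 47% |

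The documents give no value for d. Using arrival alone removes this particular effect.

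**The case against.** The strongest reply is that the difference in duration is disclosed and partly intended. The background contrasts the laboratory with real-world altitude and its combined stressors. Section 11.1 names duration as a primary factor that differs and says such differences are informative in themselves. On that aim, the night is part of the terrestrial exposure and not simply a bias. This has force for the next-day visit as a contrast in its own right. It does not rescue the sleep hypothesis, and it does not say which visit the model uses: the disclosure leaves the hypotheses and factors unchanged.

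Four stronger readings are tempting but not supported:

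- A reader might infer that the plan pools the two hut visits and so mixes exposure times. No section says so, and an arrival-only analysis is compatible with sections 11.1 and 11.4.2. The terrestrial level is undefined; exposure is unequal only if the next-day visit or both visits are used.
- A reader might take the equal-time condition as a rule for every outcome. It closes a discussion of altitude sickness, sleep, mood, drowsiness, muscle and brain oxygenation and cognition, and should be cited for those.
- A reader might quote 9.75% as the expected error. It needs independent tests, whereas both contrasts use the same simulated session in the same people.
- A reader might state the exposure difference as a multiple. The length of the hut stay is not given. An assumed 12 to 20 hours would be 720/90 = 8 to 1,200/90 ≈ 13 times the 90-minute maximum, but that range rests on the assumption.

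**Conclusion.** The point holds in two parts. As designed, the simulated-versus-terrestrial sleep hypothesis cannot be answered in any of the 24 planned participants; this follows from the visit table alone and needs no assumption. The terrestrial level of Situation is also unspecified across two visits with unequal exposure. Choosing between them after seeing the data would put the type I error per outcome at about 8–9%, if the two contrasts correlate at 0.5–0.8. The rejection rates for a next-day comparison illustrate the direction and possible size of the problem; they are not estimates for this trial.

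Both parts should be settled before any data are examined, because they concern primary hypotheses and the primary contrast.

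**What to change.** In sections 11.1 and 11.4.2:

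1. Name the arrival visit as the terrestrial level for the simulated-versus-terrestrial contrast, as the closest available match in exposure time. State that time at altitude before the arrival session is not given, so the match is approximate.
2. Treat the next-day visit as a separate level of Situation, or as a separate secondary contrast that includes the effect of the night.
3. Withdraw the simulated-versus-terrestrial sleep hypothesis and drop the Time factor for the sleep questionnaire.
4. Report hut-night sleep descriptively. Compare it with the control session only if the questionnaire's recall period is the previous night, which the documents do not state. Note that altitude would then be confounded with an unfamiliar sleeping place.
5. State that altitude-sickness conclusions for simulated altitude apply to under two hours of exposure.

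The cost is wording and one model specification, with no new visits or data. The downside is that one primary hypothesis is dropped or reframed.
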